4.4.1.2 Unsolicited AEs

4.4.1.2.1 Presence

An observation will be considered an event if it has at least a verbatim term and is not a None intensity event.

Note: Unsolicited AEs with None intensity for a specific endpoint will not be included in the safety analysis tables but will be included in separate listings.

4.4.1.2.2 Intensity

Intensity for unsolicited AE will be derived according to the following classification:

None, Grade 1, Grade 2, Grade 3, or Missing (Unknown).

If the unsolicited AE is measurable and its preferred term is part of the list of solicited reactions, then the measurement is derived based upon and following the same rule of the intensity scales defined in the protocol for that measurable injection site or systemic reaction. Note the intensity could be considered as "None" (not a reaction) in the analysis despite being considered a reaction by the investigator.

Intensity for the other unsolicited AEs will correspond to the value reported in the CRF.

The maximum intensity corresponds to the highest intensity for a unique term.

4.4.1.2.3 Last Vaccination

Last vaccination before an unsolicited AE is derived from the start date of the unsolicited AE provided in the CRF and is calculated as follows:

- If an unsolicited AE has a complete start date and different to any of the vaccination dates, the start date is used to determine the last vaccination before the unsolicited AE.
- If the start date is missing or partially missing, or equal to any vaccination date, then the visit number in the "Appeared after Visit" is used to determine the last vaccination before the unsolicited AE.

4.4.1.2.4 Time of Onset

Time of onset is derived from the start date of the unsolicited AE provided in the clinical database and the date of last vaccination as described in Section 4.4.1.2.3:

Time of Onset = start date of the unsolicited AE - date of last vaccination before the unsolicited AE

The time of onset is considered as missing only if one or both dates are missing or partially missing.

The unsolicited AEs will be analyzed "Within 30 days" after each vaccination, which corresponds to AEs with a time of onset between 0 and 30 days after each vaccination or missing onset date. An AE with missing time of onset will be considered to have occurred just after the last vaccination (computed according to the Section 4.4.1.2.3), so will be included in these tables.

Time of onset period is displayed as D0-D3, D4-D7, D8-D14, D15 or later, and Missing.

Note: Unsolicited AEs that occurred before vaccination (negative time of onset) or with onset higher than defined above (e.g, >30 days after each vaccination for non-serious AE) will not be included in analysis, but will be listed separately.

4.4.1.2.5 **Duration**

Duration is derived from the start and end dates of the unsolicited AE:

Duration = End date of unsolicited AE - start date of unsolicited AE + 1.

The duration is considered as missing only if one or both of the start and end dates of the unsolicited AE is missing or partially missing.

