9.3.2.2 Safety Endpoints

The observational endpoints for the evaluation of safety are:

- Occurrence, nature (Medical Dictionary for Regulatory Activities [MedDRA] preferred term), duration, intensity, and relationship to vaccination of any unsolicited systemic AEs reported in the 30 minutes after vaccination

- Occurrence, time of onset, number of days of occurrence, intensity, action taken, and whether the reaction led to early termination from the study, of solicited (prelisted in the subject’s diary card and CRB) injection site reactions occurring up to D07 after vaccination
- Occurrence, time of onset, number of days of occurrence, intensity, action taken, and whether the reaction led to early termination from the study, of solicited (prelisted in the subject’s diary card and CRB) systemic reactions occurring up to D07 after vaccination
- Occurrence, nature (MedDRA preferred term), time of onset, duration, intensity, action taken, relationship to vaccination (for systemic AEs only), and whether the event led to early termination from the study, of unsolicited AEs up to D30 after vaccination
- Occurrence, nature (MedDRA preferred term), time of onset, duration, seriousness criteria, relationship to vaccination, outcome, and whether the event led to early termination from the study, of SAEs (including AESIs) throughout the study

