4.3.2.3.3 Unsolicited Adverse Events

In addition to recording solicited reactions, subjects / parents / LARs will be instructed to record any other medical events that may occur during the 30-day period after vaccination. Space will be provided in the diary card for this purpose.

Information on SAEs will be collected and assessed throughout the study, from the time of vaccination until Day 30 after vaccination. Any SAE occurring at any time during the study will be reported by the Investigator in the CRB according to the completion instructions provided by the Sponsor; this includes checking the "Serious" box on the AE CRF and completing the appropriate Safety Complementary Information CRFs. All information concerning the SAE is to be reported either as part of the initial reporting or during follow-up reporting if relevant information became available later (eg, outcome, medical history, results of investigations, copy of hospitalization reports). In case a subject experiences febrile convulsion (neurological event associating fever and seizure), the assessment will be performed according to the "Guideline for definition and collection of cases of febrile convulsion", and this event will be considered an SAE. See the protocol for further details on SAE reporting.

For each unsolicited AE (whether serious or non-serious), the following information is to be recorded:

- Start and stop dates^a
- Intensity of the event:

.

The stop date of all related AEs will be actively solicited. For other events, the Investigator will provide the stop date when it becomes available. AEs for which no stop date was obtained during the course of the study will be considered as ongoing at the end of the study.

For measurable unsolicited AEs that are part of the list of solicited reactions, the size of the AE as well as the temperature for fever will be collected and analyzed based on the corresponding scale used for solicited reactions (see Table 4.1, Table 4.2, and Table 4.3).

All other unsolicited AEs will be classified according to the following intensity scale:

- Grade 1: A type of AEs that is usually transient and may require only minimal treatment or therapeutic intervention. The event does not generally interfere with usual activities of daily living.

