4.4.1.1.6 Overall Number of Days of Occurrence

If a reaction is ongoing at the end of the solicited period, then the overall number of days of occurrence after each vaccination is derived from the daily intensities and the stop date of the reaction after the end of the solicited period. The overall number of days of occurrence is:

(End date – last vaccination date) + (number of days of occurrence within the solicited period) – length of the solicited period + 1

If the end date of the solicited reaction is missing or is incomplete (contains missing data), the overall number of days of occurrence will be considered as Missing.

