5.3.1.4 Start Date and End Date

Missing or partially missing start dates or end dates for unsolicited AEs (including SAEs) will remain missing and not be imputed. If the start date is missing or partially missing, the time of onset will be considered to be missing. Nevertheless, unsolicited AEs with missing time of onset will be included in analyses according to the last vaccination (computed according to the Section 4.4.1.2.3). If either the start date or end date is missing or partially missing, the duration will be considered missing.

Missing or partially missing end dates for ongoing solicited AEs will remain missing and not be imputed.

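### The SAP sets the duration of unsolicited AEs with no end date to Missing, merging ongoing events with lost dates, so the known durations run short by an unknown amount

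*SAP*

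**What the plan says.** Protocol 9.3.2.2 lists duration among the attributes of unsolicited AEs: "Occurrence, nature (MedDRA preferred term), time of onset, duration, intensity, action taken, relationship to vaccination (for systemic AEs only". It lists duration again for SAEs, and SAP 4.3.2.2 repeats both. SAP 5.1.3.2.2 summarises subjects with unsolicited AEs by duration, among other items, and SAP 5.7 confirms that this summary now covers serious as well as non-serious events.

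SAP 4.4.1.2.5 computes duration as end date minus start date plus 1. It then says: "The duration is considered as missing only if one or both of the start and end dates of the unsolicited AE is missing", and adds partially missing dates. SAP 5.3.1.4 agrees: "If either the start date or end date is missing or partially missing, the duration will be considered missing". It also excludes imputation: "Missing or partially missing start dates or end dates for unsolicited AEs (including SAEs) will remain missing and not be imputed".

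The footnote to SAP 4.3.2.3.3, like its counterpart in Protocol 9.3.2.3.3, reads the same absent date differently: "AEs for which no stop date was obtained during the course of the study will be considered as ongoing at the end of the study". On collection it says: "The stop date of all related AEs will be actively solicited". For other events the investigator gives the date if and when it is available.

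For a solicited reaction that continues past the solicited period, SAP 4.4.1.1.6 says that without a complete end date "the overall number of days of occurrence will be considered as Missing". SAP 4.4.1.1.5 still counts days within D0 to D7, and 4.4.1.1.7 still derives an ongoing status.

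**The concern.** One section of the SAP gives an absent stop date a meaning (the event is ongoing) and another removes that meaning (its duration is Missing). An end date is most likely to be absent when the event outlasts the observation period, so the missingness is related to the length being measured. A summary of known durations then describes mainly events that ended in time to be dated, and a reader cannot tell a persistent event from a clerical gap.

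What is at stake is the description of how long unsolicited events last, in a study meant to support licensing. AEs judged unrelated are the most exposed, because their stop dates are not actively sought.

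**Working it through.** The SAP gives no figure to reproduce, so the check has three parts.

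**1. Apply the rule.** An AE that starts on D5 and ends on D9 has duration 9 − 5 + 1 = 5 days. An AE that starts on D5 with no end date has duration Missing, although the footnote calls it ongoing at study end.

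**2. Compare with the SAP's handling of neighbouring variables.**
- Time of onset for unsolicited AEs (4.4.1.2.4) has stated display periods, including a Missing row.
- Solicited reactions (4.4.1.1.7) have an ongoing / not ongoing / missing variable.
- Duration of unsolicited AEs has no display categories, no ongoing status and no stated Missing row.

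For solicited reactions, the formula in 4.4.1.1.6 is (end date − vaccination date) + days within the period − period length + 1. With all 8 days of D0 to D7 affected and an end on D10, it gives 10 + 8 − 8 + 1 = 11 days. With no end date the result is Missing, even if 4.4.1.1.7 has already classed the reaction as ongoing past D7.

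**3. Direction and possible size.** From the documents: Visit 2 falls 30 to 44 days after vaccination, and unsolicited AEs are analysed with onset from D0 to D30. Assumed, because the documents give no AE durations: onset day uniform on 0 to 30, Visit 2 day uniform on 30 to 44, and exponential durations with mean m rounded up to whole days. An AE is dated if onset + duration − 1 ≤ Visit 2 day. If nothing is followed past Visit 2, the Missing share is the average of exp(−(Visit 2 day − onset + 1)/m). At m = 14 this is 3.553 (average of exp(onset/14)) × 0.06945 (average of exp(−(Visit 2 day + 1)/14)) = 0.247.

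Simulation of 2,000,000 AEs (days):

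| Assumed m | True mean (rounded up) | Missing, none followed | Known mean | Missing, half followed | Known mean | Mean if unresolved AEs are cut at Visit 2 and averaged in (none followed) |
|---|---|---|---|---|---|---|
| 3 | 3.53 | 1.9% | 3.41 | 1.0% | 3.47 | 3.46 |
| 7 | 7.50 | 9.2% | 6.33 | 4.6% | 6.94 | 6.82 |
| 14 | 14.51 | 24.7% | 9.13 | 12.3% | 12.20 | 10.92 |
| 30 | 30.46 | 49.0% | 11.49 | 24.6% | 24.03 | 15.54 |

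With none followed, the shortfall in the mean is 3.53 − 3.41 = 0.12, 7.50 − 6.33 = 1.17, 14.51 − 9.13 = 5.38 and 30.46 − 11.49 = 18.97 days. With half followed to resolution it is 0.06, 0.56, 2.31 and 6.43 days. The direction is always short. The last column shows that averaging lower bounds with completed durations does not repair the mean.

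**The case against.** Several points limit this, and most of them stand.

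- **An absent stop date does not prove persistence.** The footnote is a convention. An unrelated AE that resolved, but whose date was never obtained, is also called ongoing. The simulation treats every undated AE as unresolved, so it shows a mechanism and does not estimate this trial. This stands, and it is why any minimum duration must carry its assumption.
- **Follow-up past study end exists.** Protocol 5.1.4.2 follows AEs that are related, or that led to discontinuation, until they resolve, stabilise or become chronic. SAP 4.3.2.3.5 has the investigator report a date of disappearance or of chronicity for AEs likely to be related. A reader might infer that chronic events in general drop out; the documents do not support that. The SAP does not say, however, whether a chronicity date serves as an end date, and other unrelated AEs are not covered.
- **Removal from the table is not stated.** A reader might infer that AEs with Missing duration leave the duration table or its denominator. The SAP neither says this nor rules it out. The events still count in the occurrence, intensity, onset and preferred-term summaries, so persistent events are not shown to be under-counted there.
- **Solicited reactions are largely protected.** It would be wrong to read the rule as covering every adverse event. Days within D0 to D7 and the ongoing status are derived without an end date; only the overall number of days is lost.
- **A partial end date usually means that the event ended.** Running such an event to Visit 2 could overstate its duration, so the remedy must leave partial dates alone.

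None of this removes the inconsistency between the footnote and the derivation, or the lack of any ongoing category for unsolicited AEs.

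**Conclusion.** The point holds in a limited form. For unsolicited AEs, SAEs included, the SAP merges events with no stop date, which it elsewhere calls ongoing, with lost or partial dates. To the extent that absent end dates mark events that outlast follow-up, the known durations run short. The exposure is mainly in unrelated AEs.

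The size is unknown. It rests on assumed durations, on undated events being unresolved, and on how many are followed to resolution: negligible at an assumed mean of 3 days, a shortfall of 2.31 to 5.38 days at a mean of 14, and larger beyond that. The documents do not show that AEs in this trial last long enough for the gap to matter.

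The endpoint is observational with no hypothesis tested, and the same rule applies in every group. The primary non-inferiority conclusion is unaffected.

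**What to change.** In SAP 4.4.1.2.5 and 5.3.1.4:
- For an unsolicited AE with a complete start date and a wholly absent end date, report duration in a separate category: *Ongoing / no stop date obtained (at least x days to last visit or termination)*. Keep it in the denominator, and label x as a lower bound that assumes the event was still present.
- State whether a recorded chronicity date is used as the censoring date.
- Keep Missing for absent or partial start dates and for partial end dates.

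In SAP 4.4.1.1.6: for a solicited reaction already classed as ongoing under 4.4.1.1.7 and with no end date, show the overall number of days as *ongoing past D7* instead of Missing.

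The cost is SAP wording and a small change to the duration derivations and table rows; no new data are needed. The drawback is that these entries are lower bounds, so they need their own row and must not be averaged with completed durations.

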4.4.1.2.6 Serious Adverse Events

An event will be considered as a serious event if "Yes" is checked for "Serious" in the CRF.

SAEs will be analyzed throughout the study using the following periods:

- Within 7 days after vaccination
- Within 30 days after vaccination
- During the study (i.e., all SAEs occurred during the study)

4.4.1.2.7 Adverse Events of Special Interest

An event will be considered as an AESI if "Yes' is checked for "Is the event an AESI?" in the CRF. AESIs will be analyzed throughout the study using the following periods:

- Within 7 days after vaccination
- Within 30 days after vaccination
- During the study (i.e., all AESIs occurred during the study)

4.4.1.3 Other Safety Endpoints

4.4.1.3.1 Pregnancy

This information will not be included in the analysis but will be listed separately. No derivation or imputation will be done.

4.4.1.3.2 Action Taken

This information will be summarized as collected, including missing observations. No derivation or imputation will be done.

4.4.1.3.3 Seriousness

This information will be summarized as collected. No derivation or imputation will be done.

4.4.1.3.4 **Outcome**

This information will be summarized as collected. No derivation or imputation will be done.

4.4.1.3.5 Causality Relationship

This information will be summarized as collected. Missing causal relationship will be handled as described in Section 5.3.1.2. Relationship to study procedure is only presented in the listing.

4.4.1.3.6 Adverse Events Leading to Study Discontinuation

This information will be summarized as collected. A flag is available in the clinical database for all AEs in order to identify AEs leading to discontinuation.

In general, the items that are counted are:

- Disposition table: A subject who, on the "Completion at End of Study" form question "What was the subject's status?" has "Adverse Event" checked.
- Safety overview table: A subject who has either on the "Completion at End of Study" form, question "What was the participant's status?" has "Adverse Event" checked or lists a solicited AE that has "Caused Study Termination" checked that is at least Grade 1 or an unsolicited AE that has "Caused Study Discontinuation" checked that is at least Grade 1 or missing and is within the time period indicated.
- System Organ Class (SOC)/Preferred Term (PT) table: A solicited AE that has "Caused Study Termination" checked that is at least Grade 1 or an unsolicited AE that has "Caused Study Discontinuation" checked that is at least Grade 1 or missing and is within the time period indicated.

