4.3.2.2 Safety Endpoints

The observational endpoints for the evaluation of safety are:

- Occurrence, nature (Medical Dictionary for Regulatory Activities [MedDRA] preferred term), duration, intensity, and relationship to vaccination of any unsolicited systemic AEs reported in the 30 minutes after vaccination
- Occurrence, time of onset, number of days of occurrence, intensity, action taken, and whether the reaction led to early termination from the study, of solicited (prelisted in the subject's diary card and CRB) injection site reactions occurring up to D07 after vaccination
- Occurrence, time of onset, number of days of occurrence, intensity, action taken, and whether the reaction led to early termination from the study, of solicited (prelisted in the subject's diary card and CRB) systemic reactions occurring up to D07 after vaccination
- Occurrence, nature (MedDRA preferred term), time of onset, duration, intensity, action taken, relationship to vaccination (for systemic AEs only), and whether the event led to early termination from the study, of unsolicited AEs up to D30 after vaccination
- Occurrence, nature (MedDRA preferred term), time of onset, duration, seriousness criteria, relationship to vaccination, outcome, and whether the event led to early termination from the study, of SAEs (including AESIs) throughout the study

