4.4 Derived Endpoints: Calculation Methods

4.4.1 Safety

4.4.1.1 Solicited Reactions

4.4.1.1.1 Daily Intensity

All daily records for solicited injection site and systemic reactions will be derived into daily intensity scales according to the following classification: None, Grade 1, Grade 2, Grade 3, or Missing (Unknown).

For the derivation of daily intensities, the following sequential steps will be applied:

1) Solicited reactions (except Fever/Pyrexia) with CRF presence recorded as "No" and with all daily records missing (Unknown), then all daily intensities will be derived as None.

2) For non-measurable (NM) solicited reactions, daily intensities will correspond to daily records reported in the clinical database. For measurable solicited reactions the daily measurements reported in the clinical database will be converted based upon the intensity scales defined in the protocol; this assumes a reaction that is too large to measure (NM) is Grade 3. Note the intensity could be considered "None" (not a reaction) in the analysis despite being considered a reaction by the investigator.

Note: The maximum intensity on the ongoing period is derived from the record of the maximum intensity/measurement after the end of the solicited period following the rule described above.

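### A solicited reaction that ended participation but has no grade is left out of the SOC/PT discontinuation table, while an ungraded unsolicited AE is kept

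*SAP*

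**What the plan says.** SAP 4.4.1.3.6, on AEs that end study participation, opens with a general statement that begins "This information will be summarized as collected. A flag is available in the clinical database for all AEs in order to identify AEs leading to". It then defines three tables.

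- **Disposition:** uses only the end-of-study form, and counts a subject whose status there is Adverse Event.
- **Safety overview:** counts a subject whose form "has 'Adverse Event' checked or lists a solicited AE that has" its termination box ticked at Grade 1 or above. It also counts a subject with a flagged unsolicited AE, graded or ungraded.
- **SOC/PT:** has no route through the form. On the solicited side it counts "a solicited AE that has 'Caused Study Termination' checked that is at least Grade 1". On the unsolicited side it counts an AE with the matching box "checked that is at least Grade 1 or missing and is within the time period indicated".

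The wording shared by the last two tables counts a solicited AE with its termination box "checked that is at least Grade 1 or an unsolicited AE that has 'Caused Study Discontinuation' checked that is at least Grade 1 or missing".

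Three other parts of the SAP bear on this. Section 4.4.1.1.3 derives the presence of a solicited reaction from its maximum grade, and sends reactions with missing presence to listings instead of tables. Section 4.4.1.2.1 treats an unsolicited observation as an event if it has a verbatim term and is not graded None. Section 4.3.2.2 makes early termination part of the solicited-reaction endpoint: "action taken, and whether the reaction led to early termination from the study, of solicited" reactions.

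**The concern.** Both halves of the rule start from the same kind of fact: a box on the case report form recording that this event ended participation. One half keeps the event when the grade is blank and the other drops it. The SAP gives no reason, and the filter sits uneasily with the promise in the same section to summarize the information as collected.

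It also runs against the way the SAP treats other blanks. A missing causality for an unsolicited systemic AE is taken as related (5.3.1.2), and an unsolicited AE with missing onset stays in the 30-day analysis (4.4.1.2.4). For a flagged solicited reaction, a blank in a secondary field removes the event from the table.

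At stake is whether the tables agree and whether the cause is shown. A reader could see a subject discontinued for an adverse event in the disposition and overview tables and find no corresponding event in SOC/PT.

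**Working it through.** The plan gives no figure to reproduce here, so the check applies the counting rules case by case.

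**Inputs**

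- Counting rules for the three tables: SAP 4.4.1.3.6.
- Solicited grade: derived from daily records (4.4.1.1.1), with the maximum taken over the period (4.4.1.1.2).
- When a solicited grade stays Missing: step 1 of 4.4.1.1.1 converts all-blank records to None only when presence is recorded as No, and not for fever. A reaction recorded as present with every daily grade blank is not converted and remains Missing.
- Grade None: possible for solicited reactions (4.4.1.1.1) and for measurable unsolicited AEs on the solicited list (4.4.1.2.2). Unsolicited AEs graded None go to listings (4.4.1.2.1).

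**Rules applied** (event box ticked, event inside the time window)

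| Event | Grade | Form says Adverse Event | Disposition | Overview | SOC/PT |
|---|---|---|---|---|---|
| Solicited | Missing | No | no | no | **no** |
| Solicited | Missing | Yes | yes | yes | **no** |
| Unsolicited | Missing | No | no | yes | **yes** |
| Unsolicited | Missing | Yes | yes | yes | **yes** |
| Solicited | None | No | no | no | no |
| Solicited | None | Yes | yes | yes | no |
| Unsolicited | None | No | no | no | no |
| Unsolicited | None | Yes | yes | yes | no |
| Either | 1 or higher | No | no | yes | yes |
| Either | 1 or higher | Yes | yes | yes | yes |

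The two event types differ only in the Missing rows. With a missing grade, SOC/PT always omits the solicited reaction and always includes the unsolicited AE. The overview differs only when the form does not say Adverse Event. The None rows are the same for both types.

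**Size of one omission.** The documents give no expected number of such cases, so one case is assumed. The interval is exact (Clopper-Pearson), the method the SAP names for safety percentages: lower limit = Beta quantile 0.025 with parameters x and n − x + 1 (0 when x = 0); upper limit = Beta quantile 0.975 with parameters x + 1 and n − x.

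| Denominator | Case omitted (x = 0) | Case counted (x = 1) |
|---|---|---|
| 100 (each adult group) | 0% (0 to 3.62) | 1.0% (0.03 to 5.45) |
| 233 (each paediatric group) | 0% (0 to 1.57) | 0.43% (0.01 to 2.37) |
| 466 (233 + 233, paediatric groups combined by vaccine) | 0% (0 to 0.79) | 0.21% (0.01 to 1.19) |

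For x = 0 the upper limit reduces to 1 − 0.025^(1/n); with n = 100 this is 3.62%. The denominators are planned enrolment, not the final safety set.

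**The case against.** The best defence is that 4.4.1.3.6 carries forward two definitions already in the SAP. A solicited reaction exists for analysis only if its derived grade shows presence (4.4.1.1.3). An unsolicited AE needs only a verbatim term and a grade other than None (4.4.1.2.1). This explains where the difference comes from, and it stands that far. It does not settle the matter: the presence rule decides who enters the analysis of a reaction, whereas a discontinuation table counts a recorded flag, which needs no grade.

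The defence also limits the reach of the point, and the following readings are not supported.

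- **That the reaction disappears from the report.** It leaves the table but goes to a listing under 4.4.1.1.3.
- **That the subject is lost from the count.** Protocol 5.2.9 tells the investigator to record Adverse Event when a voluntary withdrawal is for safety concerns, and Protocol 5.2.11 ranks that reason first. A site that follows these ticks the box feeding both disposition and overview.
- **That small redness or swelling at age 10 and over is treated unequally.** A measurement under 25 mm has no grade there, and SAP 4.4.1.1.1 accepts this: "Note the intensity could be considered 'None' (not a reaction) in the analysis despite being considered a reaction by the investigator". An unsolicited AE graded None is excluded in the same way.
- **That families who leave because of a reaction typically return no diary, so the missing grades are informative.** This is conceivable but not shown. One day at Grade 1 or above is enough (SAP 4.4.1.1.2). Sites are to complete safety follow-up after AE terminations (Protocol 5.2.12), clarify diary gaps verbally (Protocol 13.2) and report information not in the diary (Protocol 11.1).
- **That one vaccine is favoured.** The rule is the same in every group.

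**Conclusion.** The inconsistency is real but narrow. A solicited reaction flagged as ending participation, with a missing derived grade, is always left out of the SOC/PT discontinuation table. An unsolicited AE in the same position is always included. The tables can therefore disagree, and the reaction responsible is not named in any of them.

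This is a minor point and a cheap improvement. It affects descriptive safety tables only; no hypothesis or decision rule uses the count, and the primary analysis is unaffected. That cases will be few is a judgement, since the failure needs an investigator who ticked the termination box for a named reaction with no usable daily grade. The intervals above assume a single case and show only what one omission does to one group's row.

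A reader might go further and conclude that every flagged solicited reaction should be tabulated, including those graded None. The documents do not support that as a correction: 4.4.1.1.1, 4.4.1.1.3 and 4.4.1.2.1 consistently treat None as no event for analysis, and tabulating such events could give a term more discontinuations than reactions.

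**What to change.** In SAP 4.4.1.3.6, in both the safety overview and the SOC/PT bullets, change the solicited clause so that a reaction with the termination box ticked counts when its derived grade is at least 1 or missing, matching the unsolicited clause. State that this is an exception to the listing rule in 4.4.1.1.3, limited to these discontinuation tables. No grade is imputed; the recorded flag is simply counted.

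Add a footnote to both tables giving the number of flagged solicited or unsolicited events graded None, with a pointer to the listing. That lets a reader reconcile SOC/PT with disposition and overview without tabulating events that the SAP defines as no reaction.

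The cost is a short SAP edit, one program filter and a footnote. The discontinuation count may come out slightly higher.
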